6.14. Planned Exploratory Analyses

Exploratory analyses/data mining will be carried out on imaging data, fibrotest data, gene-expression data, MAP data, blood biomarkers data and tumor-tissue data as appropriate, investigating links between these data and clinical and PD efficacy endpoints. In addition, analyses between serological hepatitis status, dose adjustment and clinical outcome will be explored as appropriate. Definition of serological hepatitis status using Hepatitis B and C serology and panels will be defined in the Analysis Data Model (ADaM) and/or Table Figure Listing (TFL) programming specifications. Using serological hepatitis status in the analysis is in addition to the primary analyses using disease etiology which includes Hepatitis B and Hepatitis C. The data will be investigated if there is a major difference between frequencies of hepatitis status defined by disease etiology and serological assessment.

6.15. Annual Report Analyses

The Annual Report is replaced by the Development Safety Update Report (DSUR). The following reports will be produced for the DSUR:

- Exposure
- Disposition
- Demographics
- Listing of subjects who died during the DSUR period
- Discontinuations due to adverse event during the DSUR Period.

For further details on these reports, see the DSUR collaboration site:

http://lillynetcollaboration.global.lilly.com/sites/GMRS_GPS/Surv/dsur/default.aspx?PageView=Shared

6.16. Clinical Trial Registry Analyses

Additional analyses will be performed for the purpose of fulfilling the Clinical Trial Registry (CTR) requirements.

Analyses provided for the CTR requirements include the following:

Summary of adverse events, provided as a dataset which will be converted to an XML file. Both Serious Adverse Events and ‘Other’ Adverse Events are summarized: by treatment group, by MedDRA Preferred Term.

- An adverse event is considered ‘Serious’ whether or not it is a treatment emergent adverse event (TEAE).
- An adverse event is considered in the ‘Other’ category if it is both a TEAE and is not serious. For each Serious AE and ‘Other’ AE, for each term and treatment group, the following are provided:
 - the number of participants at risk of an event
 - the number of participants who experienced each event term
 - the number of events experienced.
- Consistent with www.ClinicalTrials.gov requirements, ‘Other’ AEs that occur in fewer than 5% of patients/subjects in every treatment group may not be included if a 5% threshold is chosen (5% is the minimum threshold).
- AE reporting is consistent with other document disclosures for example, the CSR, manuscripts, and so forth.

7. References

Appendix 1. List of Protocol Violations for H9H-MC-JBAS

Table 1. Description of Significant Protocol Violations

Category of Significant Protocol Violation/Violation Details	Methods of Identification
Violation of key inclusion/exclusion criteria (Protocol Section 7.1 and 7.2)	
General	Identified both by CRA during monitoring and programmatically, if “Failure to Meet Randomization Criteria” is marked on CRF but patient moves on to Visit 1.
Criteria [1], [8] – [28]	Identified solely by CRA during monitoring
Criteria [2]	Identified both by CRA during monitoring and programmatically, if stage is not Child-Pugh Stage A in CLIP CRF.
Criteria [3]	Identified both by CRA during monitoring and programmatically, if baseline tumor measurements in CRF data indicate tumor is measurable based on RECIST v1.1.
Criteria [4]	Identified both by CRA during monitoring and programmatically, if CRF data indicate the Age <= 18 yrs at Visit 0.
Criteria [5]	Identified both by CRA during monitoring and programmatically, if the date of informed consent is missing or it is after the Visit 1 date.
Criteria [6]	Identified both by CRA during monitoring and programmatically. Potential violations are identified programmatically, if central laboratory data do not meet required levels at Visit 1.
Criteria [7]	Identified programmatically, if CRF data indicate ECOG scale >1 at Cycle 1 (Visit 1)
Significant patient assessment or management issues	
Incorrect treatment assignment based on AFP and portal vein thrombosis levels	Identified both by CRA during monitoring and programmatically, if dynamic randomization schedule is available for cross-checking.
Study drug not omitted in the case of indicated AEs which are considered at least possibly related to study treatment	Identified both by CRA during monitoring and programmatically. Patients with the following central laboratory data results and associated treatment-related AEs will be listed for further review: ANC <0.5 10 ⁹ /L (duration of longer than 7 days to be checked by CRA) ANC <1.0 10 ⁹ /L (temperature to be checked by CRA: those with a single temperature of >101°F/38.3°C or a sustained temperature of >100.4°F/38°C for more than 1 hour) Platelet count <25 10 ⁹ /L. CTCAE Grade 3 or 4 nonhematologic toxicity. CRA will check that study drug is omitted from time of AE onset until adequate resolution (in the case of hematological toxicity, the definition of resolution is according to the investigator's opinion).
LY 2157299 dose reductions not occurring as specified	Identified both by CRA during monitoring and programmatically. dose reduction did not occur after qualifying AE >1 dose reduction (without reescalation) during the course of the study or, if reescalated, >1 dose reduction after reescalation during the course

	of the study >1 reescalation occurs during the course of the study Patient not withdrawn from LY2157299 if dosing is delayed for >2 weeks for treatment-related AEs
Lack of subject compliance with treatment	Identified both by CRA during monitoring and programmatically. List any subjects with compliance per cycle that is <80% or >120%.
Prohibited concomitant therapy	Identified both by CRA during monitoring and programmatically by verifying no prohibited medications are in CRF data. other anti-cancer therapy (chemotherapy, target therapy, radiotherapy, except palliative radiation to non-target lesions); immunotherapy; hormonal cancer therapy; experimental/investigational medication; Rapamycin analogues; Increased immunosuppressive therapy (patients on maintenance immunosuppressive therapy after liver transplant are eligible); At the discretion of the investigator, hormone-refractory prostate cancer patients who are stable on GnRH agonist therapy and breast cancer patients who are stable on antiestrogen therapy (for example, and aromatase inhibitor) may have that treatment continued while they are enrolled in this study.
Failure to perform PK collections	Identified both by CRA during monitoring and programmatically. Note: only collections “not done” are considered significant protocol violations.
Failure to perform safety assessments	Failure to perform safety procedures or missing safety measurements per requirements in Study Schedule (Attachment 1 in Protocol). Hematology/chemistry; CT and MRI ECG ECHO and Doppler Identified both by CRA during monitoring and programmatically. Note: only collections “not done” are considered significant protocol violations.
Failure to perform efficacy assessments	Failure to perform efficacy procedures or missing efficacy measurements. Radiological Tumor Assessments per RECIST and mRECIST. Palpable/visible (as applicable). Identified both by CRA during monitoring and programmatically. Note: only collections “not done” are considered significant protocol violations.
Violation of discontinuation criteria	
Discontinuation criteria met but patient not removed from study (see Protocol Section 7.3.1)	Identified both by CRA during monitoring and programmatically: Discontinuation CRF data indicate criteria was met Lab data or the CRF AE page indicate that the subject was pregnant during the treatment. If echocardiography with Doppler data indicate moderate or severe heart valve toxicities are observed and patient is not removed from study.
Verify that the investigator has signed the CRF for all subjects who have screen failed, early discontinued, or completed the trial.	Identified both by CRA during monitoring and programmatically, if subject discontinued and Casebook Signature CRF is not completed.

Other	
Patient received drug that was declared “not Fit for Use”	Identified solely by CRA during monitoring.
Inadvertent un-blinding	Identified solely by CRA during monitoring.
Drug dispensing errors	Identified solely by CRA during monitoring.
Maintenance and calibration issues with critical equipment	Identified solely by CRA during monitoring. Verify maintenance and calibration records are current during the study for the following critical equipment: ECHO with Doppler Imaging Machines (CT/MRI) ECG If Applicable at site: DCE-MRI and/or DW-MRI Equipment needed to extract optional biopsy tissue
Other protocol violations that result in study discontinuation	As recorded on the CRF discontinuations page.

Abbreviations: AE = adverse event; CRA = clinical research associate; CRF = case report form; CT = computed or computerized tomography; DCE = Dynamic Contrast Enhanced; DW = diffusion weighted; ECG = electrocardiogram; ECHO = echocardiogram; MRI = magnetic resonance imaging.

Leo Document ID = b8cb3cf7-15b0-40a1-8f2d-8cd00cf2a27b

Approver: PPD

Approval Date & Time: 26-Jul-2017 01:50:30 GMT

Signature meaning: Approved

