#### **10.4.1. Samples for Study Qualification and Health Monitoring**

Blood, urine, and tissue samples will be collected to determine whether patients meet inclusion/exclusion criteria and to monitor patient health. A serum pregnancy test will be performed (if applicable). Other clinical laboratory tests will be analyzed by central and local laboratories. [Attachment 2](#) lists the specific tests that will be performed for this study. Patient eligibility is based on local laboratory results only, unless the investigator chooses to use the central laboratory for such a purpose. Central laboratory results are used for study report purposes and where appropriate for safety analyses.

At screening, pretreatment formalin-fixed paraffin-embedded (FFPE) tumor tissue will be collected (paraffin blocks or approximately 10 unstained slides cut from that block) for correlation studies of molecular markers and for confirmatory diagnosis. Due diligence should be used to make sure that a tumor specimen (not a normal adjacent or a tumor margin sample) is provided. Pathology notes accompanying archival tissue may also be requested.

Investigators must document their review of each laboratory safety report.

Samples collected for specified laboratory tests will be destroyed within 60 days of receipt of confirmed test results. Tests are run and confirmed promptly whenever scientifically appropriate. When scientific circumstances warrant, it is acceptable to retain samples to batch the tests run or to retain the samples until the end of the study to confirm that the results are valid. Certain samples may be retained for a longer period, if necessary, to comply with applicable laws, regulations, or laboratory certification standards.

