**Serum pregnancy test (females only)a**

Hepatitis B e antibody

Hepatitis B virus DNA

Hepatitis C RNA

Abbreviations: AFP = alpha-fetoprotein; aPTT = activated partial prothrombin time; BNP = brain natriuretic peptide; ECG = electrocardiogram; INR = international normalized ratio; LDH = lactate dehydrogenase; MAP = multi-analyte panel; PF4 = platelet factor 4; PIVKA II = prothrombin induced by vitamin K absence; PT = prothrombin time; RBC = red blood cell; TGF- $\beta$  = transforming growth factor beta; WBC = white blood cell.

- a All samples will be discarded within 60 days of validated test results. Validation will occur at the time of initial testing. All these tests will be performed at a local or investigator-designated laboratory, with the exception of immunophenotype.
- b All samples will be discarded within 60 days of validated test results. Validation will occur at the time of initial testing. All these tests will be performed at a Lilly-designated laboratory. Tests will be performed at a local laboratory if performed during the treatment extension period.
- c Test not performed if both chemistry and ECG chemistry are required. See [Attachment 1](#).

---

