6.12.3. Clinical Laboratory Evaluation

Table [JBAS.6.6](#) describes the clinical laboratory tests to be performed and whether the test will be performed locally or centrally:

Table JBAS.6.6. Clinical Laboratory Tests

Hematology^a	Clinical chemistry^b
Hemoglobin	Serum concentrations of:
Erythrocyte count (RBC)	Total bilirubin
Leukocytes (WBC)	Direct bilirubin
Neutrophils, segmented + bands	Total protein
Lymphocytes	Alkaline phosphatase
Monocytes	LDH
Eosinophils	Creatine kinase
Basophils	Alanine aminotransaminase/serum glutamic pyruvic transaminase
Platelets	Aspartate aminotransferase/ Serum glutamic oxaloacetic transaminase
	Blood urea nitrogen
Immunophenotype^b	Creatinine
Urinalysis^a	Uric acid
Specific gravity	Calcium
pH	Glucose, random (nonfasting)
Protein	Albumin
Glucose	Cholesterol
Ketones	Phosphorus
Blood	Sodium
Leukocyte esterase	Potassium
	Magnesium
ECG chemistry^b	Serum markers^b
Lipase	AFP
Thyroid stimulating hormone	AFP L3
Tri-iodothyronine	PIVKA II
Thyroxine	E-cadherin
Calcium ^c	
Glucose, random (nonfasting) ^c	TGF-β+PF4^b
Albumin ^c	Coagulation^b
Phosphorus ^c	aPPT
Sodium ^c	PT
Potassium ^c	INR
Magnesium ^c	
Special chemistry^b	Fibrotest^b
Cystatin C	Urine C-terminal telopeptides of Type 1 Collagen^b
Troponin I	
BNP	MAP^b
High-sensitivity C-reactive protein	Serum pregnancy test (females only)^a
Hepatitis B and C serology and panels^b	
Hepatitis B surface antigen	
Hepatitis B surface antibody	
Total hepatitis B core antibody	
Hepatitis B e antigen	
Hepatitis B e antibody	
Hepatitis B virus DNA	
Hepatitis C RNA	

Clinical Laboratory Tests (Abbreviations)

Abbreviations: AFP = alpha-fetoprotein; aPTT = activated partial prothrombin time; BNP = brain natriuretic peptide; ECG = electrocardiogram; INR = international normalized ratio; LDH = lactate dehydrogenase; MAP = multi-analyte panel; PF4 = platelet factor 4; PIVKA II = prothrombin induced by vitamin K absence; PT = prothrombin time; RBC = red blood cell; TGF- β = transforming growth factor beta; WBC = white blood cell.

- a Performed at local laboratory.
- b Performed at central laboratory. Performed at a local laboratory if performed during the treatment extension period.
- c Test not performed if both chemistry and ECG chemistry are required.

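### SAP Appendix 1 screens ANC, platelets and hemoglobin in central laboratory data although scheduled hematology is local, so the programmed violation check would miss most or all scheduled counts

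*SAP*

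**What the plan says.** SAP Appendix 1, Table 1, sets out how each significant protocol violation is found. Two rows matter here.

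- **Study drug not omitted after a qualifying event.** The row opens "Identified both by CRA during monitoring and programmatically". It then defines the list: "Patients with the following central laboratory data results and associated treatment-related AEs will be listed for further review". The hematologic triggers are ANC below 0.5, ANC below 1.0 and platelets below 25 (all x10^9/L). Alongside the first is the note "duration of longer than 7 days to be checked by CRA", and the second has a similar note for temperature. Grade 3 or 4 nonhematologic toxicity is a further trigger.
- **Inclusion criterion [6], adequate organ function.** The programmed part reads: "Potential violations are identified programmatically, if central laboratory data do not meet required levels at Visit 1".

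Three other places say where these values come from.

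- SAP Section 6.12.3, Table JBAS.6.6, gives hematology, including neutrophils, platelets and hemoglobin, footnote a: "Performed at local laboratory". Central testing is footnote b, which hematology does not carry.
- Protocol Attachment 2 gives hematology its own footnote a: "All these tests will be performed at a local or investigator-designated laboratory, with the exception of immunophenotype".
- Protocol Section 10.4.1 says: "Patient eligibility is based on local laboratory results only, unless the investigator chooses to use the central laboratory for such a purpose".

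**The concern.** A prespecified check names as its input a dataset that, under the same plan, is not where the scheduled values sit. The check audits the protocol's rule in Section 9.4.1.1 for withholding LY2157299 during hematologic toxicity. SAP Section 6.12.9 classes these violations as significant because they bear on data integrity and patient safety.

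A programmer who follows Appendix 1 to the letter would get a short or empty hematologic list, and a reader of the study report could take that for good adherence. Criterion [6] has the same fault: its ANC, platelet and hemoglobin limits would be checked in data that do not routinely contain those tests.

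**Working it through.** No formula applies, and the documents give no figure for this check. The test is whether the named source can hold the values the rule needs.

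1. **Values needed.** The omission screen needs on-treatment ANC and platelets. Criterion [6] needs pre-treatment ANC, platelets and hemoglobin, together with bilirubin, transaminases, PT/INR and creatinine or creatinine clearance.

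2. **Where scheduled hematology is run.** It is local in SAP Table JBAS.6.6, and local or investigator-designated in Protocol Attachment 2. The two documents agree, and Appendix 1 is the outlier.

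3. **Other routes by which central counts could exist.**
   - Protocol Attachment 3 has a hepatic hematology panel that includes neutrophils and platelets and is assayed centrally. It is optional and is drawn only after a treatment-emergent hepatic abnormality, so it does not screen systematically for cytopenia.
   - Section 10.4.1 lets the investigator choose the central laboratory for eligibility, which could give some central screening values.
   - Neither route covers the scheduled on-treatment counts.

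4. **Criterion [6], component by component.** Bilirubin, transaminases, creatinine and PT/INR carry the central footnote in Attachment 2, so central values should exist for them. ANC, platelets and hemoglobin do not carry it. The data-source conflict is therefore confined to the hematology part. Because eligibility is local by default, a central chemistry value may still not be the one on which the patient was admitted.

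5. **Timing for criterion [6].** Protocol Section 10 equates Cycle 1 with Visit 1. In the Attachment 1 schedule as extracted, hematology and serum chemistry appear at baseline (within 7 days) and next on Cycle 1 Day 8, with no Day 1 sample. Visit 1 values would then be taken after treatment has started. Two qualifications apply:
   - The coagulation row does show a Cycle 1 Day 1 sample.
   - The note to criterion [6] calls for repeat tests before Cycle 1 Day 1 dosing when a result is slightly out of range, so some patients may have a later pre-dose value.

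6. **Are the local values available to the program?** SAP Section 6.12.3 plans a listing of all hematology and CTCAE grading of the relevant results. As scheduled hematology is local, those local values must reach the reporting data for that listing to be produced. The documents do not say by what route.

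**The case against.** The strongest reply is that this is a wording slip in one of two detection routes. Much of that stands.

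- **Monitoring is a parallel route.** The row names the CRA as well as the program, and its last step has the CRA check omission from the onset of the adverse event, which does not depend on a laboratory list. SAP Section 6.12.9 has violations in the monitoring database exported for use by statistics, so cases found by the CRA can reach the listing.
- **Some central counts may exist**, from the hepatic panel or from central eligibility testing.
- **A broader programmed check is described.** Section 6.12.9 says CRF data in general are checked by program and leaves the details to specifications that are not part of these documents. This does not repair the rule: the documents do not say that local hematology is entered on the CRF, and Appendix 1 is the specific instruction.
- **Other output shows severe cytopenias.** The listing and grading under Section 6.12.3 do not depend on Appendix 1. They would not show whether drug was withheld.

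A reader might infer that the programmed check can find no case at all, or that the violation listing and the per-protocol population are bound to be incomplete. The documents support neither. A central hepatic-panel value could trigger the list, the nonhematologic item does not depend on hematology, and monitoring can supply the missed cases. What the objection does not answer is that, for scheduled counts, one of the two planned routes looks in the wrong place.

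**Conclusion.** The inconsistency is real and should be corrected. As written, the programmed screen would miss most or all scheduled ANC, platelet and hemoglobin values, leaving these violations to CRA monitoring. The number of patients affected cannot be estimated from the documents.

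The effect on inference is small. The primary overall survival analysis uses the randomized population and does not depend on this check. Under SAP Sections 6.1.1 and 6.12.9, both the per-protocol analysis and exclusion for a significant violation are optional. What is at stake is the reliability of the violation listing and how a short list would be read.

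The conclusion assumes that Table JBAS.6.6 and Attachment 2 describe what is actually done. If scheduled hematology is in fact also sent to a central laboratory, those two places are the ones to correct. The timing point for criterion [6] is less certain, because it rests on a schedule table that may have been damaged in extraction.

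**What to change.** In SAP Appendix 1:

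1. Name the local hematology results already listed and graded under Section 6.12.3 as the source for the ANC and platelet screen and for the hematology part of criterion [6].
2. For criterion [6], replace the Visit 1 value with the last pre-dose value from the laboratory used for eligibility.
3. Reconcile Appendix 1 with Table JBAS.6.6 and Protocol Attachment 2. If central hematology data do exist, say which.

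The cost is a few lines of SAP text and a change of input dataset in the violation program. It should need no new data collection, provided the local values reach the reporting data as Section 6.12.3 implies. The thresholds and the rules for withholding treatment stay as they are.
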